8.3. Adverse Events and Serious Adverse Events

Progression of the cancer under study is not considered an adverse event.

The definitions of an AE and SAE can be found in Appendix 3 (Section 10.3). The definition of AESI can be found in Section 8.3.5.

AEs will be reported by the subject (or, when appropriate, by a caregiver, surrogate, or the subject's legally authorized representative).

The investigator and any qualified designees are responsible for detecting, documenting, and recording events that meet the definition of an AE, SAE, or AESI. Investigators remain responsible for following up AE, SAEs and other reportable safety events for outcome.

8.3.1. Time Period and Frequency for Collecting AE, SAE and Other Reportable Safety Event Information

All AEs, SAEs and other reportable safety events that occur after the consent form is signed but before IP administration must be reported by the investigator if the event cause the subject to be excluded from the study, or is the result of a protocol-specified intervention, including but not limited to washout or discontinuation of usual therapy, diet, or a procedure.

Table 7 below summarizes the different reporting timelines for AEs, SAEs, SUSAR, AESIs and pregnancy.

Table 7 Adverse Event Reporting Timelines to the Sponsor

Type of Event	AE	SAE / SUSAR	AESI related to IP	Pregnancy
Reporting period	From consent until 30 days after last dose of IP	From consent until 30 days after the last IP dose, and any time after that window if the SAEs are believed to be related to AL101	From consent until 30 days after the last dose of IP, or the initiation of a new anti-cancer therapy	From consent until 120 days after last dose of IP
Reporting Timelines to the Sponsor	Entered into the clinical database on an ongoing basis	Within 24 hours	Within 24 hours	Within 24 hours
Reporting Method	AE eCRF	AE eCRF	AE eCRF	Pregnancy form in eCRF

Abbreviation: Adverse event (AE), adverse events of special interest (AESI), Serious adverse event (SAE), serious unexpected suspected adverse reaction (SUSAR)

Medical occurrences that begin before the start of IP but after obtaining informed consent will be recorded on the Medical History/Current Medical Conditions section of the eCRF not the AE section.

All SAEs will be recorded and reported to the Sponsor or designee immediately and under no circumstance should this exceed 24 hours, as indicated in Appendix 3 (Section 10.3). The investigator will submit any updated SAE data to the Sponsor within 24 hours of it being available.

Investigators are not obligated to actively seek AE or SAE after conclusion of the study participation. However, if the investigator learns of any SAE, including a death, at any time after a subject has been discharged from the study, and he/she considers the event to be reasonably related to the IP or study participation, the investigator must promptly notify the Sponsor.

8.3.2. Method of Detecting AEs and SAEs

The method of recording, evaluating, and assessing causality of AE and SAE and the procedures for completing and transmitting SAE reports are provided in Appendix 3 (Section 10.3).

Care will be taken not to introduce bias when detecting AEs and/or SAEs. Open-ended and non-leading verbal questioning of the subject is the preferred method to inquire about AE occurrences.

8.3.3. Follow-up of AEs and SAEs

After the initial AE/SAE report, the investigator is required to proactively follow each subject at subsequent visits/contacts. All SAEs, and AEs of special interest (as defined in Section 8.3.5), will be followed until resolution, stabilization, the event is otherwise explained, or the subject is lost to follow-up (as defined in Section 7.4). Further information on follow-up procedures is provided in Appendix 3 (Section 10.3).

8.3.4. Regulatory Reporting Requirements for SAEs

- Prompt notification by the investigator to the Sponsor of a SAE is essential so that legal obligations and ethical responsibilities towards the safety of subjects and the safety of an IP under clinical investigation are met.
- The Sponsor has a legal responsibility to notify both the local regulatory authority and other regulatory agencies about the safety of an IP under clinical investigation. The Sponsor will comply with country-specific regulatory requirements relating to safety reporting to the regulatory authority, Institutional Review Boards (IRB)/Independent Ethics Committees (IEC), and investigators.
- For all studies investigator safety reports must be prepared for suspected unexpected serious adverse reactions (SUSAR) according to local regulatory requirements and Sponsor policy and forwarded to investigators as necessary.
- An investigator who receives an investigator safety report describing a SAE or other specific safety information (e.g., summary or listing of SAEs) from the Sponsor will review and then file it along with the IB and will notify the IRB/IEC, if appropriate according to local requirements.

8.3.5. Adverse Events of Special Interest

An AESI is one of scientific and medical interest specific to understanding of the IP and may require close monitoring and rapid communication by the investigator to the Sponsor. An AESI may be serious or non-serious. The rapid reporting of AESIs allows ongoing surveillance of these events in order to characterize and understand them in association with the use of this IP. AESI for AL101 include events that are mediated by disruption of the Notch signaling pathway and can be attributed to the drug's mechanism of action with no clear alternate etiology and which may require more frequent monitoring and/or interventions. All AESI must be reported in the AESI section of the CRFs.

AESI observed with AL101 are detailed in the sections below and include hepatic function abnormalities, colitis, infusion reactions (including anaphylaxis), keratoacanthoma, and hepatic toxicities including drug induced liver injury (DILI). For treatment of these AESIs, please refer to Section 6.4.

8.3.5.1. Colitis

In study CA216001, DLTs consisting of Grade 3 colonic ulceration/Grade 3 diarrhea were reported, both indicating the potential for development of colitis. Intestinal inflammation is thought to be an on-target effect that requires close monitoring and potential dose reductions. Intense abdominal pain, severe diarrhea and the presence of blood and/or mucous in the stools are indicative of potential colitis. Signs and symptom of colitis should prompt work up to rule out an infectious etiology. The gold standard for the diagnosis of colitis pathological and thus requires a biopsy, but in the absence of an infectious etiology, colitis should be the exclusion diagnosis. For management of colitis see [Table 4](#).

8.3.5.2. Infusion Reactions (including Anaphylaxis)

In study CA216001 1 subject developed Grade 3 anaphylaxis, a DLT at the 4 mg dose.

For infusion reactions, refer to Section [6.4.1](#)

8.3.6. Disease Progression

Clinical signs or symptoms associated with progression of underlying malignancy are not reported as AEs if they are clearly consistent with the suspected progression of the underlying malignancy. Clinical symptoms of progression may be reported as AEs if the symptom cannot be determined as exclusively due to the progression of the underlying malignancy or does not fit the expected pattern of progression for the disease under study. The site should report clinical signs/symptoms that have met the SAE definition within 24 hours of learning the event if the etiology is not clear at the time of the onset. If the subsequent workup has revealed that the reported event is associated with progression of underlying malignancy, the follow-up

information should be submitted, and event term should be updated to the cause that lead to the hospitalization instead of disease progression. For example, if a subject is hospitalized with shortness of breath that is determined to be associated with worsening of pleural effusion during the subsequent workup, pleural effusion could be used an event term instead of disease progression.

If there is any uncertainty about an AE being due only to the disease under study, it should be reported as an AE or SAE.

8.3.7. Death Events

All death events will require completion of a death data collection page within the eCRF.

Timelines for reporting of death events are identical to the requirements for SAE reporting. Events resulting in death will be an SAE regardless of association to disease progression (Section 10.3.5). Death is an outcome and should not be reported as an event term. The event that lead to the death should be reported as the SAE term.

8.3.8. Pregnancy

- Details of all pregnancies in female subjects and female partners of male subjects will be collected as outlined in Appendix 4 (Section 10.4).
- If a pregnancy is reported, the investigator should inform the Sponsor within 24 hours of learning of the pregnancy and should follow the procedures outlined in Appendix 4 (Section 10.4).
- Abnormal pregnancy outcomes (e.g., spontaneous abortion, fetal death, stillbirth, congenital anomalies, ectopic pregnancy) are considered SAEs.

8.4. Biomarkers and Pharmacokinetics

8.4.1. Activating Notch Alteration Detection by NGS Assay

The planned use of a commercially available NGS assay, LDT or other validated IUO clinical trial assay capable of detecting activating genetic alterations in the *NOTCH 1/2/3/4* genes is to identify for inclusion those subjects most likely to benefit from therapy with AL101.

Notch mutational status from prior tests with commercially available or LDT NGS assay as assessed at enrollment may be confirmed centrally. In the US, any FDA-cleared/approved, validated CTA, or LDT NGS assay is acceptable. In Europe any commercially available CE marked device can be used.

For questions, please contact the Sponsor's Medical Monitor.

8.4.2. Pharmacokinetics

Blood samples for PK will be obtained at the times designated in the SoA, footnote p (Table 1). Start- and end-time for each investigational product infusion (and any interruptions) will be recorded in the eCRF. In addition, the actual time of the sample collection will be recorded in the eCRF. All samples will be analyzed for both parent and metabolite using liquid chromatography with tandem mass spectrometry (LC-MS/MS) assay.

Analysis will be conducted to assess the PK characteristics of AL101 at the first dose and at steady state, and to determine whether any of the following covariates — age, body size, sex, organ impairment, drug-drug interaction — influence the PK of AL101.

For more details on instructions for collecting PK samples, refer to the Study Laboratory Manual.

8.4.3. Other Biomarkers

Predictive biomarkers of response or resistance to the IP will be explored, such as but not limited to:

- IHC: Tumor specimens will be stained for the NICD and potentially other biomarkers.
- NGS: Mutational analysis will be performed in tumor tissue samples and potentially in blood (cfDNA, CTCs).

Biomarkers indicative of drug activity may be explored, such as but not limited to:

- CTC enumeration.
- Expression of pharmacodynamic biomarkers of Notch inhibition in tumor tissue and/or CTCs.

Samples may be stored according to local regulations following the last subject's last visit for the study at a facility selected by the Sponsor to enable further analysis of biomarker responses to AL101.

8.4.4. Sample Collection

Tumor tissue and blood will be collected at the times designated in the SoA (Section 1.3).

Any biopsy should not exceed the risk associated with a simple excisional, incisional or core biopsy. Tumor tissue for biomarker analysis will be required for study participation at screening (block or 25 unstained slides). Tumor biopsies will also be taken at Cycle 4 Day 1 \pm 28 days. Screening biopsies may be fresh, or archival from within 2 years. On-treatment biopsies do not need to be done if either the site investigator or person performing the biopsy judges that no tumor is accessible for biopsy or that biopsy poses too great of a risk to the subject. (If the only tumor accessible for biopsy is also the only lesion that can be used for RECIST v1.1 response evaluation, then the subject may be exempt from biopsy after discussion with the Sponsor).

The Laboratory Manual will provide details on biomarker sample collection.

8.5. Genetics

Germline genetics are not evaluated in this study.

8.6. Unscheduled Visits

There may be a need to have a subject return to clinic for an unscheduled visit for a variety of reasons, including but not limited to repeat of a lab test, evaluation of an AE, or evaluation of

disease status. Any procedure that is conducted during a regularly scheduled on-treatment visit may be performed at an unscheduled visit and will be recorded in the eCRF.

9. STATISTICAL CONSIDERATIONS

9.1. Statistical Hypothesis and Sample Size Determination

The study will utilize the Simon two-stage optimal design (Figure 1 and Table 8) and will include up to 67 to 73 subjects, depending on IP dose evaluated in Stage 1 and Stage 2 as follows:

- if the AL101 dose is 6 mg QW throughout the study, there will be up to 67 subjects evaluated, including the 6 subjects in the lead-in cohort for the Stage 1 evaluation.
- if AL101 4 mg is evaluated in Stage 1 and Stage 2, there will be up to 73 enrolled subjects consisting of up to 67 subjects at AL101 4 mg and 6 subjects in the lead-in cohort of AL101 6 mg. Note, the lead-in cohort will not be included in the Stage 1 evaluation.

In both scenarios there will be up to 26 evaluable subjects in Stage 1, and 41 additional evaluable subjects in Stage 2 provided at least 4 subjects (out of 26) responded in Stage 1.

While the data on Stage 1 is maturing, Stage 2 will continue enrolling an additional 41 subjects, unless an unexpected safety signal emerges that in the judgement of the DMC requires analysis and/or poses a serious threat to the well-being of the subject. This decision will be made in agreement with the Sponsor.

If no more than 3 subjects respond in Stage 1, the study will be stopped for futility. If 4 or more subjects respond, Stage 1 will be considered positive. For the entire study (Stages 1 and 2), the null hypothesis will be rejected if 15 or more responses are observed in 67 subjects. Only the Efficacy Evaluable set of subjects will be counted toward this analysis. This design has 80% power at the 5% type I error level to detect a desirable success rate of 23% against the null hypothesis of an unacceptable success rate of 11%. The success rate parameters for the two-stage design are aligned with recent published experience of clinical studies (Twelves, 2014). If at the end of Stage 1, there are 4 responses in the Notch-activated TNBC subjects, the study will continue to Stage 2.

Table 8 Sample Size Hypothesis

Total	Look1	Futility Boundary		Attained	Attained	Probability of	Expected
							Sample Size
(n)	(n_1)	Look1	Look2	Alpha	Power	Early	H0 (EN0)
		(r_1)	(r_2)			Stopping	
67	26	3	11	0.049	0.807	0.681	39.1

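### Section 9.1 gives two incompatible final success rules: 15 or more responses of 67 in the text (57% power) and 12 or more in Table 8 (81% power)

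*Combined protocol and SAP*

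**What the plan says.** All the relevant statements are in protocol Section 9.1.

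- **Sample sizes:** "up to 26 evaluable subjects in Stage 1, and 41 additional evaluable subjects in Stage 2", 67 in total.
- **Stage 1 rule:** "If no more than 3 subjects respond in Stage 1, the study will be stopped for futility". Four or more responses count as a positive Stage 1.
- **Final rule in the text**, for both stages combined: "the null hypothesis will be rejected if 15 or more responses are observed in 67 subjects".
- **Claimed operating characteristics:** "This design has 80% power at the 5% type I error level". The target response rate is 23% and the null rate is 11%.
- **Table 8 row:** "67 26 3 11 0.049 0.807 0.681 39.1". In column order this is n = 67, n1 = 26, r1 = 3, r2 = 11, attained alpha 0.049, attained power 0.807, probability of early stopping 0.681, and expected sample size under the null 39.1.

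Section 9.3 adds that the Simon two-stage rule is the only significance test in the study.

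**The concern.** In Table 8, r1 and r2 are both headed as futility boundaries. The text reads r1 = 3 as stop at 3 or fewer and continue at 4 or more. Read the same way, r2 = 11 means failure at 11 or fewer and success at 12 or more. The text sets the final cut-off three responses higher but attaches to it the power that belongs to Table 8.

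Because this is the only formal test, the choice of cut-off decides whether the trial is positive. Totals of 12, 13 or 14 responses (17.9% to 20.9% of 67) are a success under one statement and a failure under the other. The study is open-label and single-arm, so an unresolved rule could end up being settled once the response count is known.

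**Working it through.** **Inputs (all from Section 9.1).** p0 = 0.11, p1 = 0.23, n1 = 26, n2 = 41, n = 67, r1 = 3. The final cut-off k is 12 (Table 8, r2 + 1) or 15 (text).

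**Formulas.** Let X1 ~ Bin(26, p) be the Stage 1 responses and X2 ~ Bin(41, p) the Stage 2 responses.

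- Probability of early stopping: PET(p) = P(X1 ≤ 3)
- Expected sample size: EN(p) = 26 + (1 − PET(p)) × 41
- Probability of rejecting the null: R(p; k) = Σ over x = 4 to 26 of P(X1 = x) × P(X2 ≥ k − x)
- Alpha = R(0.11; k); power = R(0.23; k)

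**Step 1: reproduce Table 8 with k = 12.**

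- PET(0.11) = 0.0483 + 0.1553 + 0.2399 + 0.2372 = 0.6807 (table 0.681)
- EN(0.11) = 26 + 0.3193 × 41 = 39.09 (table 39.1)
- Alpha = R(0.11; 12) = 0.0494 (table 0.049)
- Power = R(0.23; 12) = 0.8069 (table 0.807)

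All four figures agree. A search over two-stage designs for 11% against 23%, with alpha at most 0.05 and power at least 0.80, also returns 3/26 and 11/67 as the Simon optimal design.

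**Step 2: apply the rule in the text.**

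| Reject if responses of 67 are at least | Alpha | Power at 23% |
|---|---|---|
| 12 (Table 8) | 0.0494 | 0.8069 |
| 13 | 0.0255 | 0.7489 |
| 14 | 0.0120 | 0.6696 |
| 15 (text) | 0.0051 | 0.5728 |

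**Step 3: size of the discrepancy.**

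- Loss of power: 0.8069 − 0.5728 = 0.2341. This is the probability, at a true rate of 23%, of passing Stage 1 and finishing with 12, 13 or 14 responses.
- Chance of missing a drug with a true rate of 23%: 1 − 0.5728 = 0.427 under the text and 1 − 0.8069 = 0.193 under Table 8. Both include the same 0.120 chance of stopping at Stage 1.
- Solving R(p; 15) = 0.80 gives p = 0.266. The text rule reaches 80% power only at a true response rate of about 26.6%.

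**Step 4: other readings of 15.**

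- Ignoring the Stage 1 stop, 15 or more of 67 gives alpha 0.0055 and power 0.5945.
- Counting Stage 2 responses only, 15 or more of 41 gives power 0.030. The text in any case counts both stages together.

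Neither reading brings the cut-off of 15 near 80% power.

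**The case against.** The strongest reply is that the trial is not shown to be underpowered. Section 9.1 introduces the design by reference to Figure 1 and Table 8, and Section 9.3 ties the test to that pre-defined design. The Table 8 boundary could therefore be the operative one and the sentence with 15 a slip. It is fair that power is 57% or 81% depending on which statement governs. However, the sentence with 15 is the only explicit rejection rule in the text, so a reader following it would apply 15.

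The text rule is also conservative. Its alpha of 0.005 lies well inside 5%, so it cannot increase false positives. That is correct, and it means that the power claim is what fails, along with the attained alpha in Table 8. The protocol nowhere says that it chose a 0.5% error rate at the price of 57% power.

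Third, the higher bar may be deliberate: 15/67 is 22.4%, close to the 23% target. It may equally be an error, for example adding the 4 Stage 1 responses to the boundary of 11. The documents settle neither, so the sponsor must say which number is intended.

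Finally, Section 9.3 says the SAP will be finalized before database lock and that major changes will also appear in a protocol amendment. This limits the scope for a late choice of rule but does not remove the contradiction. Figure 1 is not visible in the text reviewed. Whatever it shows, it cannot make both rules in Section 9.1 true.

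**Conclusion.** The concern holds. The text rule (15 or more) and the Table 8 boundary (12 or more) cannot both be the final criterion, and the claimed 80% power is true only for 12 or more. Under 15 or more, power at 23% is 57.3% and alpha is 0.0051. The discrepancy costs 23.4 percentage points of power and more than doubles the chance of rejecting a drug that meets the target, from 19% to 43%.

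These figures assume 67 efficacy-evaluable subjects if Stage 2 is completed, 26 of them in Stage 1, and a binding Stage 1 stop at 3 or fewer responses, as Section 9.1 specifies. The binding stop matters for the Table 8 rule: without it, alpha at 12 or more would be 0.060. Because this is the study's only significance test, the point must be corrected.

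**What to change.** State one final rule and make every statement agree with it.

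- **To keep the Table 8 design:** in Section 9.1 change the final cut-off from 15 to 12 or more responses in 67. The 80% power, 5% type I error and all Table 8 entries then stand. This is the only cut-off that matches the stated operating characteristics.
- **If 15 is intended:** change r2 in Table 8 to 14, and restate alpha as about 0.005 and power as about 57% in both the text and the table. If 80% power at 23% is still wanted with that stricter rule, the design has to be re-derived.

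Check Figure 1 and the SAP for the same number. Make the change by protocol amendment, not in the SAP alone, and before the response data are reviewed for the final decision.

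The first option costs one number and no added patients. The second adds no patients if 57% power is accepted; otherwise its cost depends on the redesign.

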9.2. Analysis Populations

The following analysis sets will be used in this study:

- Safety analysis population: All subjects who receive at least one dose of IP (even a partial dose).

- Efficacy evaluable population: All subjects who receive at least one dose of IP at the dose as determined by the lead-in cohort, have measurable disease at baseline per RECIST v1.1, and have at least one post-baseline on-study assessment of tumor response, unless there is documented clinical progression after discussion with Sponsor's Medical Monitor or radiological progression prior to Week 8.
- Per-protocol (PP) analysis population: All efficacy evaluable subjects who have no major protocol violations, as defined by the Sponsor prior to database lock.

Note: if there is a discrepancy between the Notch-activated mutation determination between commercial/LDT NGS assay and the confirmatory central assay, the subject will be non-evaluable for the Efficacy and PP evaluations.

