All subjects will receive premedication with H1- and H2-blockers (refer to Section [6.6.1](#)) and corticosteroids as prophylaxis (refer to Section [6.6.2](#)). Toxicity post-AL101 administration will be managed as specified in Section [6.4](#).

During the treatment period, subjects will undergo radiographic assessments every 8 weeks (± 3 days) for review by the investigator. Radiographic scans will also be collected and held for possible future retrospective independent evaluation. Other assessments will be done as specified in the Schedule of Activities ([Table 1](#)). A repeat of tumor imaging will be required for the purposes of confirmation of response (i.e., partial response, and/or complete response). The confirmation scan should be no earlier than 4 weeks following the first indication of response.

Samples from tumor biopsies will be collected at screening from a locally advanced or metastatic lesion (fresh or archival within 2 years), and at Cycle 4 Day 1 ±28 days (provided that biopsy collection is medically safe and not contraindicated). If an archival tumor block or 25 unstained slides are not available, the subject will be required to have a fresh tumor sample obtained at screening. Biopsy samples will be evaluated by NGS for genomics, immunohistochemistry (IHC) for Notch intracellular domain (NICD) stain, and other biomarkers potentially related to sensitivity to AL101 or TNBC prognosis. Blood samples for pharmacokinetics (PK) and biomarker analysis will also be collected on the same day as the on-treatment biopsy.

All subjects will undergo end of study (EOS) visit 30 days post last treatment with IP and will be contacted to determine survival status at timepoints specified in study duration. In subjects who discontinued IP due to toxicity, radiographic imaging will be done every 3 months until disease progression or until the subject initiates another anti-cancer therapy.

Disclosure Statement

This is a single group treatment study with no masking.

Number of Subjects

Using the Simon two-stage optimal design (targeting a response of 23% or greater), up to 67 to 73 subjects will be enrolled, depending on IP dose evaluated in Stage 1 and Stage 2 as follows:

- if the AL101 dose is 6 mg QW throughout the study, there will be up to 67 subjects evaluated, including the 6 subjects in the lead-in cohort for the Stage 1 evaluation.

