9.3.3. Efficacy

9.3.3.1. Definitions of Efficacy Endpoints

Primary: ORR, defined as the proportion of subjects who have a best overall response (BOR) of CR or PR as determined using RECIST v1.1. BOR is defined as the best response recorded between the date of first dose of IP and the date of subsequent anti-cancer therapy. A BOR of CR or PR requires confirmation of the assessment no earlier than 4 weeks later.

Other efficacy endpoints are as follows:

- Progression free is defined as the interval from the start of study treatment to the earlier of the first documentation of disease progression or death from any cause.
- Clinical Benefit Response is defined as SD+PR+CR.
- DOR, defined as the interval from the first documentation of CR or PR to the earlier of the first documentation of disease progression (per RECIST v1.1) or death from any cause.
- OS, defined as the time from the date of start of treatment to the date of death from any cause. Subjects who are lost to follow-up and those not known to have died by the cut-off date for analysis will be censored on the date the subject was last known alive, or the data cut-off date, whichever is earlier.

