9.3.3.2. Analysis of Efficacy Endpoints

For primary and secondary endpoints refer to Section 1.2.

The primary efficacy endpoint is the ORR based on the proportion of subjects with an overall response of either CR or PR. Disease response will be assessed using RECIST v1.1. Primary efficacy analysis will be performed on the Efficacy Evaluable population.

Secondary endpoints include CBR, DOR, PFS, PFS at 6 months, and OS. Secondary efficacy analysis will be performed on the Efficacy Evaluable population and Per Protocol population.

Efficacy endpoints will also be analyzed for each of the sub-populations: TNBC subjects as well as non-TNBC subjects.

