9.4. Interim Analyses

Because a Simon two-stage optimal design will be employed, ORR will be assessed during Stage 1 for subjects who have received IP for at least 2 cycles (8 weeks) and no more than 8 cycles (8 months). While the data on Stage 1 is maturing, Stage 2 will continue enrolling an additional 41 subjects for a total of 67 subjects, unless an unexpected safety signal emerges that in the judgement of the DMC requires analysis and/or poses a serious threat to the well-being of the subject.

The Statistical Analysis Plan will describe the planned analyses in greater detail.

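### ORR is analysed only in the Efficacy Evaluable set, and CBR, PFS, 6-month PFS and OS only in that set and its Per-Protocol subset, so early deaths without a scan or documented progression drop out; no all-treated efficacy analysis is specified

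*Combined protocol and SAP*

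**What the plan says.** Section 9.2 defines three sets. The Safety population is everyone who received any investigational product (IP). The EE set requires treatment at the selected dose, measurable disease at baseline, and that subjects "have at least one post-baseline on-study assessment of tumor response, unless there is documented clinical progression" (after discussion with the Medical Monitor) or radiological progression before Week 8. The Per-Protocol set is the part of EE without major violations. A note adds that a subject whose central Notch result disagrees with the enrolling assay is evaluable in neither efficacy set.

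The sets are used as follows:

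- **Simon test (9.1):** "Only the Efficacy Evaluable set of subjects will be counted toward this analysis".
- **ORR (9.3.3.2):** "Primary efficacy analysis will be performed on the Efficacy Evaluable population".
- **CBR, DOR, PFS, 6-month PFS and OS (9.3.3.2):** "Secondary efficacy analysis will be performed on the Efficacy Evaluable population and Per Protocol population".
- **Safety population:** safety analyses (9.3.4), disposition (9.3.1) and baseline tables (9.3.2). No efficacy use is stated.

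Section 9.3.3.1 defines PFS as "the interval from the start of study treatment to the earlier of the first documentation of disease progression or death from any cause", and OS from start of treatment to death from any cause.

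Replacement of non-evaluable subjects is not addressed. Section 9.1 says "there will be up to 26 evaluable subjects in Stage 1, and 41 additional evaluable subjects in Stage 2", while the Synopsis says "up to 67 to 73 subjects will be enrolled" and Section 9.4 says "Stage 2 will continue enrolling an additional 41 subjects for a total of 67 subjects". The Synopsis and 9.1 each count in evaluable terms in one place and in enrolled or total terms in another.

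**The concern.** EE membership depends on what happens after the first dose. For a survival endpoint that starts at first dose, this deletes some of the earliest events. A death in Week 5 with no scan and no recorded progression is a PFS event and an OS event under 9.3.3.1, yet 9.2 removes the subject from both curves. For ORR and CBR, an unscanned subject cannot be a confirmed responder or have documented stable disease, so removal shrinks the denominator and never the numerator.

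In a single-arm trial the reported rate and curve are the result, with no control arm carrying the same exclusion. Readers will set them against outside figures that may cover all treated patients.

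**Working it through.** **1. Who is left out.** The End of Study visit includes imaging (Table 5). Section 7.2 continues tumor assessment after discontinuation for reasons other than progression, and Table 5 adds scans every 3 months after discontinuation for toxicity. Most toxicity discontinuers therefore gain a post-baseline scan and enter EE. What remains is mainly death, withdrawal or loss before any scan, without documented progression.

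**2. Direction, by type of exclusion.**

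| Excluded subject | ORR, CBR | PFS | OS |
|---|---|---|---|
| Early death, no scan, no documented progression | raised | lengthened | lengthened |
| Lost or withdrawn, no scan, no known death | raised | little effect (would be censored near time zero) | uncertain |
| Discordant central Notch result | either way | either way | either way |

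**3. The plan's own figure.** Inputs from 9.1 and Table 8: n1 = 26, r1 = 3, n = 67, r2 = 11, p0 = 0.11, p1 = 0.23. With b(x; n, p) the binomial probability and c the number of responses needed to reject,

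P(reject) = Σ over x = 4 to 26 of b(x; 26, p) · P(X2 ≥ c − x), X2 ~ Bin(41, p).

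For c = 12 (Table 8): 0.0494 at p0 and 0.807 at p1, matching the stated 0.049 and 0.807. For c = 15 (text of 9.1): 0.0051 and 0.573. That conflict between text and table is a separate matter; both boundaries are carried below.

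**4. ORR.** The documents give no non-evaluable share d, so 5%, 10% and 15% are assumptions. Step 1 suggests the upper values may be high.

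- *Without replacement:* 12 responders among 67 treated is 17.9%. In EE it reads 12/64 = 18.8%, 12/60 = 20.0% or 12/57 = 21.1%. The rejection rule is a count and the dropped subjects contribute no responses, so type I error stays 0.049 (≥12) or 0.005 (≥15).
- *With replacement:* 67/(1 − d) = 70.5, 74.4 or 78.8 subjects are treated, and 12/67 in EE corresponds to 17.0%, 16.1% or 15.2% of all treated. If 11% is also an all-treated rate, the EE null rate is 0.11/(1 − d) = 0.116, 0.122 or 0.129. P(reject) is then 0.068, 0.092 or 0.126 for ≥12, and 0.008, 0.013 or 0.021 for ≥15.

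**5. OS, illustration only.** Section 2.1 gives a median survival of 13 to 24 months. Section 2.2 dates the 13-month figure from recurrence or diagnosis of distant metastases, not from first dose. Taking survival as exponential with median m, and Week 8 as 56 days = 1.84 months:

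e = 1 − 2^(−1.84/m) = 0.093 for m = 13 and 0.052 for m = 24, or 6.3 and 3.5 of 67 subjects.

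If all these deaths left EE, S_EE(t) = S(t)/(1 − e) after Week 8, so median_EE = m · [1 + log2(1/(1 − e))]. This gives 14.8 instead of 13 and 25.8 instead of 24, a shift of 1.84 months in both cases. If half left, the medians are 13.9 and 24.9, a shift of about 0.9 months.

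**6. 6-month PFS.** Those deaths all fall before 6 months. Ignoring censoring, the EE proportion is the all-treated proportion times 1/(1 − e): 1/0.948 = 1.05 to 1/0.907 = 1.10 if all left EE.

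**7. Discordant Notch result.** Such a subject may have scans and may be a confirmed responder, so this exclusion can lower the Simon count. If 5%, 10% or 15% were dropped at random without replacement (assumed Stage 1/total sizes 25/64, 23/60 and 22/57; p = 0.11; ≥12), P(reject) is 0.037, 0.023 or 0.016. If the central result is known only after outcome, chance need not govern who is dropped.

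**The case against.** - **The excluded group may be small.** This stands. Imaging after discontinuation recovers most toxicity discontinuers, and some early deaths will have documented progression and stay in EE. Entry limits on ECOG status and life expectancy may also lower the early death rate. In the other direction, subjects counted from first dose after up to three metastatic lines may do worse than the median survival used above.
- **The SAP may deal with it.** Section 9.3 calls itself a summary and defers detail to a separate SAP that is not among the documents. The point is therefore limited to what they specify. Section 9.3 also says major modifications will appear in a protocol amendment, so the protocol is the right place for the change.
- **Exclusions are disclosed.** Section 9.3.1 lists reasons for exclusion from each set and 9.3 provides individual listings, so a reader could rebuild an all-treated ORR. That is disclosure, not a pre-specified analysis.
- **Evaluable-only Simon tests are common.** Agreed, and nothing here asks for that test to change.

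A reader might go further and infer that the trial's type I error exceeds 5%. The documents do not support that. It would need three things together: replacement of non-evaluable subjects, the ≥12 boundary, and 11% being an all-treated rate. None is established, and under the ≥15 rule the largest value above is 0.021. A reader might also infer that EE always flatters the drug. That holds for ORR with unscanned subjects and for PFS and OS with early deaths, not for discordant Notch results or for OS in subjects lost without a known death.

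**Conclusion.** The concern holds in this limited form. Under the stated rules, a treated subject who dies before any scan without documented progression is missing from PFS and OS curves whose definitions count that death. Unscanned subjects of any kind are missing from the ORR and CBR denominators. The bias is upward for ORR and CBR, and towards longer PFS and OS where early deaths are dropped.

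Its size is not derivable from the documents. The 1.8-month shift in median OS is an illustration that assumes exponential survival, a literature median with a different time origin, and every death before Week 8 leaving EE; with half leaving, it is about 0.9 months. The ORR shifts rest on assumed dropped shares. For unscanned subjects without replacement, the go/no-go decision does not change. The change should be made because the reported estimates are at stake and the remedy is cheap, not because a false-positive rate has been shown to be wrong.

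**What to change.** - **Sections 9.2 and 9.3.3.2, time-to-event endpoints:** analyse PFS, 6-month PFS and OS in all subjects who received any IP at the selected dose, using all available death and survival data. Keep EE and Per-Protocol as sensitivity analyses.
- **Sections 9.2 and 9.3.3.2, response endpoints:** pre-specify supporting ORR and CBR in the same all-treated set. For ORR, count no confirmed response as non-response. Show both endpoints with and without centrally discordant subjects, beside the unchanged EE-based Simon test.

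The cost is protocol and SAP wording, a few extra tables and a slightly lower supporting ORR. The Simon test keeps its design power (0.807 at ≥12 of 67). No new assessments are needed: death pages (8.3.7) and survival contacts (4.1) are already planned, though withdrawal and loss to follow-up (7.3, 7.4) will leave some subjects censored early.
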